5.3. Secondary endpoints

Secondary endpoints:

- Frequency of leakage onto clothes before and after use of test product
- Experience of leakage onto clothes compared to only using usual product
- Reliability of notifications
- Ability to move with test product
- Subjects worry of leakage before and after use of test product
- Confidence to avoid full leakage with test product compared to only using usual product
- Confidence in daily life compared to only using usual product
- Feeling of control with test product compared to only using usual product
- Control of leakage progression with test product compared to only using usual product
- Feeling of security with test product compared to only using usual product
- Evaluation of confidence to increase social activities with test product compared to only using usual product
- Evaluation of sleep with test product compared to only using usual product
- Confidence at night with test product compared to only using usual product
- Evaluation of users' preference
- Reason for preference
- Evaluation of users' peace of mind with test product
- To evaluate users' assessment of QoL with test product compared to usual product
- Adhesive residue to transmitter

- Adhesive residue to skin

Explorative endpoints:

- Change in HRQoL, Appendix 1
- Change in Ostomy Leakage Impact (OLI), Appendix 2
- Evaluation of self-management (predictability of change) of stoma appliance compared to usual product

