7.2. Flow-chart

Table 1 chart showing the connection between visits and assessments.

	Registration/measurement	PERFORMED BY	INFOR-MATION MEETING	SCREEN-ING	VISIT 1	VISIT 2 TERMI-NA-TION	CON-TINUOUS LY
	General						
	Oral information	Investigator	X				
	Written informed consent	Investigator	X	X			
	Check of in- and exclusion criteria	Investigator		X			
	Insurance of subjects' wellbeing and compliance with CIP	Investigator		X	X		
	Registration of Demographics/assessments						
	
 • Gender • Age • Weight • Height • Duration of ileostomy/colostomy (year when created) • Reason for creation of the stoma • Shape of the stoma • Size of the stoma (diameter on widest place and height) • Body profile • Physical activity • Sweat • Output • Information about the current stoma product • Normal changing pattern • Normal main reason for change of product • Stoma awareness • Technical ability • Use of accessories 	Investigator			X		
	
 ○ Wear time ○ Reason for change 	Subject					X X

No.	Registration/measurement	PERFORMED BY	INFOR-MATION MEETING	SCREEN-ING	VISIT 1	VISIT 2 TERMI-NATION	CONTINUOUS LY
	Primary endpoint						
1	To evaluate system performance focusing on accuracy of data classification into true positive and true negative	sponsor representa-tive (evaluate pic-tures, assess leak to sensors) Subject (takes pic-tures at each change)					X
	Secondary endpoint(s)						
2	Frequency of leakage onto clothes	Subject			X	X	
3	Overall experience of leakage onto clothes with test product compared to only using usual product	Subject				X	
4	Reliability of notifications	Subject				X	
5	Ability to move with test product	Subject				X	
6	Subjects worry of leakage	Subject			X	X	
7	Confidence to avoid leakage onto clothes with test product compared to only using usual product	Subject				X	
8	Confidence in daily life compared to only us-ing usual product	Subject				X	
9	Feeling of control with test product com-pared to only using usual product	Subject				X	
10	Control of leakage progression with test product compared to only using usual prod-uct	Subject				X	
11	Feeling of security with test product com-pared to only using usual product	Subject				X	
12	Evaluation of confidence to increase social activities with test product compared to only using usual product	Subject				X	
13	Evaluation of sleep with test product com-pared to only using usual product	Subject				X	

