10.1. Statistical design, method and analytical procedures

Definition of analysis populations

Intention to Treat (ITT) and Safety populations will be defined at a formal data review meeting just before database lock. As a minimum, the data manager, the clinical manager and the statistician will be involved in the classification of subjects.

The ITT population (full analysis set) will be constituted by all included subjects who:

- Have provided valid informed consent
- Have information for at least one of the endpoints

The Safety population will constitute by subjects who have given informed consent.

All statistical analysis and summaries will be based upon the ITT population whereas adverse events and Device deficiencies will be assessed based on the safety population. Invalid individual data points may be omitted from analysis even though the corresponding subject is part of the ITT population. Any exclusion of data points will be documented.

A formal PP population is not planned due to the explorative nature of the investigation. Considering the data obtained it might however be considered to make additional explorative analyses based on a subset of the ITT population.

Analysis of endpoints, individual questions and baseline data

All endpoints and individual questions as well as baseline/demographic data will be listed and summarized by descriptive statistics. Summaries can be made for 1- and 2-piece users as well as for the subgroups (flat, convex and if relevant concave) or (iPhones, Androids), if relevant.

The accuracy of the sensor performance will be calculated based on picture data used to correlate notifications given with output to sensors on baseplates (primary endpoint). The accuracy will be calculated by dividing the true positive plus the true negative with the total sum of the true positive, true negative, false positive and false negative.

For secondary endpoints where the possible answer is Yes or No, the proportion of subjects answering "Yes" will be calculated. By use of an exact test in the Binomial distribution a 95% confidence interval will be estimated for the proportion. Further, it will be tested if the proportion is significantly different from 50% when using a 5% test level. For questions answered on a 5-point scale the answers can be grouped in 2 (e.g. "higher" or "much higher" against the rest of the answers) and analyzed by the above described method.

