23.4. Appendix 4 – Questions

Assessment/endpoint	Question	Answer
Assessment		
Reason for change	What is the reason for change? Please tick ALL that apply.	
 • I follow my usual changing pattern • There is leakage under and outside the baseplate (soiling the clothes) • Due to a notification from the App • The entire baseplate is detached • The outer edge of the baseplate is detached • The center of the baseplate is detached • I am afraid the baseplate will detach • The area around the stoma is itching • The area around the stoma is painful • There is leakage under the baseplate (but not outside the baseplate) • The stoma bag is filled with air • There is a vacuum in the stoma bag • Other
Secondary endpoint(s)		
Frequency of leakage onto clothes	Think back on the last 3 weeks - how many times have you experienced leakage onto clothes?	Number
Overall experience of leakage onto clothes with test product compared to only using usual product	Compared with your usual product, to which degree have you experienced leakage onto your clothes with test product?	Fewer episodes of leakage onto clothes - More episodes of leakage onto clothes
Reliability of notifications	To which degree did you find the notifications from the App reliable and trustworthy?	Very high degree - High degree - Some degree - Low degree - Not at all
Ability to move with test product	Compared to your usual product, how was your freedom to move with test product?	Much better - better - Same - Worse - Much worse
Users worry of leakage	Think back on the last 3 weeks - to which degree have you worried about leakage?	Very high degree - High degree - Some degree - Low degree - Very low degree/Not at all

Confidence to avoid leakage onto clothes with test product compared to only using usual product	Compared to your usual product, did you feel confident that you could avoid leakage onto clothes?	Yes – No
Confidence in daily life compared to only using usual product	Compared to your usual product, to which degree did the test product give you confidence in daily life?	Much higher degree- Higher degree- Same degree - Lower degree- Much lower degree
Feeling of control with test product compared to only using usual product	Compared to your usual product, did test product give you a feeling of leakage control?	Yes, higher leakage control No, lower leakage control

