Control of leakage progression with test product compared to only using usual product	Compared to your usual product, did the test product give you a feeling of control of leakage progression?	Yes, higher control of leakage progression No, lower control of leakage progression
Feeling of security with test product compared to only using usual product	Compared to your usual product, did you feel more or less secure with test product?	I felt more secure – I felt less secure
Evaluation of confidence to increase social activities with test product compared to only using usual product	Compared with your usual product, did the test product affect your confidence to engage in social activities such as seeing friends, and do physical activities?	I felt more confident - I felt less confident
Evaluation of sleep with test product compared to only using usual product	Compared with your usual product, did the test product affect your sleep?	Yes, to the better Yes, to the worse No, the same
Confidence at night with test product compared to only using usual product	Compared with your usual product, to which degree did the test product give you confidence at night?	Much higher - Higher - Same - Lower - Much lower
Preference	Which product solution do you prefer?	Own product - Own product with test product
Reason for preference	What is your reason for preference? (Please tick all that apply)	
 • Body fit • Ability to bend and stretch • Feeling of security • Feeling of confidence • Less fear of leakage onto clothes

		
 • Discreet to wear • Discreteness in leakage control • Better sleep • Less embarrassment • Other text
Preference	How often would you use the test product?	Will never use it – Will use it rarely – Will use it sometimes – Will use it often – Will use it every day
Preference	If the test product was available today, would you start using it?	Yes – No
Preference	Would you recommend the product to others living with a stoma?	Yes – No
Evaluation of users' peace of mind with test product	To which degree did the test product give you peace of mind?	Very high degree- High degree- Low degree- Very low degree
To evaluate users' assessment of QoL with test product compared to usual product	Overall, do you think the test product can improve your feeling of control and confidence to avoid leakage onto clothes and therefore improve your quality of life?	Yes - No => if no, why not? Text

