Adhesive residue to skin	To which degree did you experience adhesive residue to the skin in the area around the transmitter?	Very low degree/Not at all - Low degree - Some degree – High degree -Very high degree
Adhesive residue to transmitter	To which degree did you experience adhesive residue on the backside of the transmitter?	Very low degree/Not at all - Low degree - Some degree – High degree -Very high degree
Exploratory endpoints		
HRQoL evaluation		See Appendix 1
OLI evaluation		See Appendix 2

Evaluation of self-management (predictability of change) of stoma appliance compared to usual product	To which degree does test product support you to control the daily routines around appliance change?	Very high degree - High degree - Some degree - Low degree - Very low degree / Not at all
Evaluation of self-management (predictability of change) of stoma appliance compared to usual product	To which degree does test product make it easier to know when to change appliance compared to own product?	Very high degree - High degree - Some degree - Low degree - Very low degree / Not at all

Signature Page for VV-0308987 v2.0

Approved	[Redacted]	29-Mar-2021 12:03:16 GMT+0000
Approved	[Redacted]	29-Mar-2021 13:35:22 GMT+0000
Approved	[Redacted] Medical / Clinical	29-Mar-2021 13:39:23 GMT+0000
Approved	[Redacted] Medical / Clinical	29-Mar-2021 14:56:10 GMT+0000

Signature Page for VV-0308987 v2.0

Document Owner: [Redacted]

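### The item on confidence to avoid leakage onto clothes opens as a comparison but ends in an undirected Yes or No, so a Yes does not unambiguously show a gain over the usual product

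*Combined protocol and SAP*

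**What the plan says.** - **Endpoint.** Row 7 of the flow-chart (section 7.2) and Appendix 4 both call it "Confidence to avoid leakage onto clothes with test product compared to only using usual product". Section 5.3 lists it as "Confidence to avoid full leakage with test product compared to only using usual product". Both labels are comparative.
- **Item.** The full question in Appendix 4 is "Compared to your usual product, did you feel confident that you could avoid leakage onto clothes". After the opening phrase, what the subject is asked to affirm or deny is "did you feel confident that you could avoid leakage onto clothes", and the answers are Yes or No with no further label.
- **Neighbouring items.** Others with the same opening carry a direction. Leakage control is answered "Yes, higher leakage control No, lower leakage control", and security is asked as "Compared to your usual product, did you feel more or less secure with test product".
- **Timing.** Row 7 has a single mark, which falls under Visit 2 as the columns read. The rows for worry and for frequency of leakage onto clothes are marked at Visits 1 and 2.
- **Analysis.** For Yes/No items, section 10.1 calculates the share of Yes with an exact 95% confidence interval, and then: "Further, it will be tested if the proportion is significantly different from 50% when using a 5% test level".
- **Use.** Section 3.1 names support for commercial claims as the reason for evaluating user experience. Section 10.4 sets no success criteria but allows results to be used for claims.

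**The concern.** The endpoint asks whether confidence changed. After its comparative opening, the item asks whether the subject felt confident, not more confident. A subject who was equally confident before can read it literally and answer Yes. One whose confidence rose from very low to moderate can answer No. Neither answer can be told apart from one given by a subject who reads the item as a true comparison.

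Because this item has no Visit 1 answer, it yields no paired change. The test against 50% then has no clear meaning: under the literal reading, 50% is not the value that represents no difference between products. At stake is whether a significant majority of Yes could be cited as improved confidence over the usual product, or whether a real improvement could be passed over.

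**Working it through.** **1. Is this item the odd one out?** Ten items in Appendix 4 open with a comparison to the usual product.

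| Item | Names the test product | Direction in the answers |
|---|---|---|
| Experience of leakage onto clothes | yes | fewer to more |
| Freedom to move | yes | much better to much worse |
| **Confidence to avoid leakage onto clothes** | **no** | **none** |
| Confidence in daily life | yes | much higher to much lower |
| Leakage control | yes | higher or lower |
| Leakage progression | yes | higher or lower |
| Security | yes | more or less |
| Social activities | yes | more or less confident |
| Sleep | yes | better, worse, same |
| Confidence at night | yes | much higher to much lower |

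Only this item lacks both features.

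**2. Inputs for the size.** The planned number is 25 subjects, with drop-outs not replaced (sections 6 and 10.2). The test is against 50% at the 5% level (section 10.1); since it is for a difference, it is taken as two-sided. The plan gives no power or expected rate for this item, so there is no figure of its own to reproduce.

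**3. Threshold.** With X the number of Yes among n = 25, the two-sided p-value for x above 12.5 is 2 × P(X ≥ x | 25, 0.5).
- x = 17: p = 0.108, not significant.
- x = 18: p = 2 × 0.0216 = 0.043, significant. The observed share is 18/25 = 72%, exact 95% CI 50.6% to 87.9%.

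**4. Chance of a significant majority of Yes under a literal reading.** Assume every subject reports absolute confidence while using the test product, and let q be the true share who would say Yes. The chance is P(X ≥ 18 | 25, q). With 20 answers the threshold is 15.

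| q | 25 answers | 20 answers |
|---|---|---|
| 40% | 0.1% | 0.2% |
| 50% | 2.2% | 2.1% |
| 60% | 15.4% | 12.6% |
| 70% | 51.2% | 41.6% |
| 75% | 72.7% | 61.7% |
| 80% | 89.1% | 80.4% |

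If the device has no effect, q equals the share confident with the usual product. The documents do not give that share, so every value of q is an assumption.

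**5. The opposite error.** The formula contains only q, the share confident with the test product. Suppose, for illustration, that confidence rose from 20% to 50% of subjects. The chance of a significant majority is still P(X ≥ 18 | 25, 0.5) = 2.2%, the same as if it had been 50% throughout. Under the literal reading the test cannot separate a gain from no change in either direction.

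**6. Comparative reading.** If subjects answer as though asked whether they were more confident, Yes means a perceived gain, and step 4 does not apply. The recorded data do not show which reading a subject used.

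**The case against.** The strongest case on the other side has five parts.

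- **The opening is comparative.** Someone who looks only at the predicate might infer that this is a plain question about being confident and that Yes shows no gain at all. The documents do not support that: the question begins with the usual product, and a subject who applies that phrase gives a valid comparative answer. The fault is ambiguity. This part stands.
- **Confidence is measured at baseline elsewhere.** A reader might infer that there is no Visit 1 measure of confidence. In fact the quality-of-life questionnaire (Appendix 1) has a confidence domain and is completed at both visits; worry about leakage is also asked at both. This stands as a correction of fact. It does not repair the item: the nearest Appendix 1 statement concerns confidence that the appliance will not leak, over seven days, whereas the sensor notifies of leakage under the baseplate and this endpoint concerns keeping it off clothes.
- **The population worries about leakage.** Inclusion criteria 8 and 9 require recent leakage problems and at least some worry, so 40% or 50% confident with the usual product is at least as arguable as 60% to 75%. At those rates a significant majority of Yes is not inflated. This stands, and is why the low rates are shown; there the error becomes a missed gain.
- **Other items cover the ground.** Security, leakage control and confidence in daily life and at night are directional. The overall quality-of-life question even asks about improved confidence regarding leakage onto clothes. This stands in part: that question bundles control, confidence and quality of life into one Yes and asks what the product can do.
- **The study is exploratory.** There are no hypotheses or success criteria, and no section names this item as a claim. This limits the consequence.

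A reader might also extend the point to the exploratory self-management question, "To which degree does test product make it easier to know when to change appliance compared to own product", whose scale cannot record harder. That extension is largely a matter of preference: a subject who finds it harder can answer at the bottom of the scale, which falls among the unfavourable answers if grouped as in section 10.1, so the favourable share is not inflated.

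**Conclusion.** The point holds as an ambiguity in one item. A Yes does not unambiguously show a gain over the usual product, a No mixes several states, and the item has no Visit 1 answer that would settle it. The planned test against 50% therefore cannot by itself establish improvement for this endpoint.

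The size depends on two unknowns: how subjects read the question, and how many would be confident anyway. If all read it literally and the device does nothing, the chance of a significant majority of Yes with 25 answers runs from 0.1% at 40% confident to 73% at 75%. If all read it comparatively, there is no distortion from this source. The upper figures should not be quoted as the false-claim rate of the study. Severity is minor: one secondary item in an exploratory study, though one whose results may be used for claims.

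**What to change.** Reword the item so that it names the test product and gives a direction, for example: *Compared with your usual product alone, how was your confidence, while using the test product, in keeping leakage off your clothes?* The answers would be much higher, higher, same, lower and much lower, which is the scale already used for confidence at night.

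State in section 10.1 that this item is analysed with the grouping given there as an example: the two higher answers against the rest, so that same counts as not favourable. A significant majority then means that more than half of subjects reported a gain.

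The cost is one changed question in the clinical trial app, with the amendment and any notification that section 12 requires for changed endpoints or assessment methods. The downside is that the favourable share may look smaller.

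If data have already been collected with the present wording, report the share of Yes with the full question beside it, and do not claim improvement over the usual product from this item alone.

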The total HRQoL score and the OLI sub scores will be analysed by a paired t-test to compare the results from Visit 1 (own product) and Visit 2 (own and test product).

The frequency of leakage on close before and after use of use of Olympus will be analysed by a Poisson loglinear model taken the paired design into consideration.

Users worry of leakage given on a 5-point scale will be analysed by a proportional odds ratio model taken the paired design into consideration to compare the results from Visit 1 (own product) and Visit 2 (own and test product)..

Other summaries and analyses can be made, if relevant.

As it is an exploratory study no adjustment for multiple testing will be applied.

All statistical analyses and summaries will be made with SAS version 9.4 (SAS Institute Inc., Cary, NC)

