10.2. Sample size

Due to the conceptual nature of this trial no formal sample size calculation has been performed. It is assumed that 25 subjects will be adequate for evaluating the sensor performance.

We strive to include an equally number of users in the categories 1pc, 2pc, flat, convex and concave.

Due to the exploratory nature of the study, drop-out subjects will not be replaced.

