10.3. Level of significance and power

If a statistical analysis is performed a significance level of 5% will be applied. As this is an exploratory study no power has been applied.

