10.4. Pass/fail criteria

No formal success criteria are applied in this investigation. Study results may be used for relevant claims.

The study will provide valuable insight into the performance and safety of the device and the ability to support the user with useful information regarding potential leakages in an everyday life setting.

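### The secondary endpoint on confidence for social activities rests on one item that joins social and physical activity, so the two cannot be told apart

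*Combined protocol and SAP*

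**What the plan says.** Section 5.3 names the endpoint as "Evaluation of confidence to increase social activities with test product compared to only using usual product". The synopsis and row 12 of the flow-chart in section 7.2 use the same label, and the flow-chart shows it answered by the subject at Visit 2 only.

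Appendix 4 (section 23.4) assigns one question to this endpoint. It asks whether, compared with the usual product, "did the test product affect your confidence to engage in social activities such as seeing friends, and do physical activities". The answer options are "I felt more confident - I felt less confident".

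For yes/no secondary endpoints, section 10.1 plans a proportion with an exact 95% confidence interval and adds that "it will be tested if the proportion is significantly different from 50% when using a 5% test level". It also states: "As it is an exploratory study no adjustment for multiple testing will be applied". Section 10.4 reads: "No formal success criteria are applied in this investigation. Study results may be used for relevant claims". Section 3.1 lists support for commercial claims among the secondary objectives.

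**The concern.** The label covers one kind of activity and the question covers two, with one answer for both. A subject whose confidence changed for exercise but not for seeing friends, or the reverse, has no answer that records this. The plan has no scoring rule for such a subject. The proportion reported under the social-activity label is therefore not a measure of what the label names, and that answer cannot be split after Visit 2.

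What is at stake is the claim. Results may be used for claims and there is no multiplicity adjustment, so a nominally significant result on this item could be carried directly into a statement about social activities that the item cannot support.

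**Working it through.** The plan states no power, effect size or expected proportion for this endpoint, so there is no figure to reproduce. The point rests on wording; the arithmetic only gives scale.

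**Label against item**
- Content: social activities in 5.3; social and physical activities in Appendix 4.
- Answers stored: one, more or less confident, for both areas together.
- Timing: once, at Visit 2.

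**What the answer can mean.** Let B be the share of subjects who gained in both areas, s the share who gained only for social activities, and p the share who gained only for physical activities. The share the label promises is S = B + s. Leave aside subjects with no change and subjects who skip the item.
- If subjects answer *more* after a gain in either area, the item records R = B + s + p, so R − S = +p (overstated).
- If subjects read the question as requiring both, the item records R = B, so R − S = −s (understated).
- With mixed readings, R − S lies between −s and +p.

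The documents give neither s nor p, and nothing tells the subject which reading to use.

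**Scale (hypothetical).** Inputs:
- N = 25 (sections 6 and 10.2), with all 25 assumed to answer. Drop-outs are not replaced.
- A 5% level (section 10.3), taken as two-sided.
- The section 10.1 test against 50%, assumed to apply to this more/less item.

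Each subject is 1/25 = 4 percentage points. The exact two-sided p-value for x above 12.5 is 2 × Σ C(25,k)/2^25, summed over k = x to 25, with 2^25 = 33,554,432.
- x = 18: the sum of C(25,k) is 726,206, so p = 2 × 726,206 / 33,554,432 = 0.043. The proportion is 72%, 95% CI 50.6% to 87.9%.
- x = 17: add C(25,17) = 1,081,575 to get 1,807,781, so p = 2 × 1,807,781 / 33,554,432 = 0.108. The proportion is 68%, 95% CI 46.5% to 85.1%.

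The threshold is therefore 18, and one subject can cross it in either direction:
- Overstated: 18 recorded, one of them a physical-only gain, so the social count is 17.
- Understated: 17 recorded, with one social-only gainer who answered *less*, so the social count is 18.

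**Range.** The chance of at least 18 *more* answers out of 25, by the probability of that answer:

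| Probability of *more* | 50% | 55% | 60% | 65% | 70% | 75% |
|---|---|---|---|---|---|---|
| Chance of 18 or more | 2.2% | 6.4% | 15.4% | 30.6% | 51.2% | 72.7% |

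- If S is 50% and an assumed further 10% answer *more* for physical activity only, the chance rises from 2.2% to 15.4%.
- If S is 70% and an assumed 10% are social-only gainers who answer *less*, the chance falls from 51.2% to 15.4%.

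With fewer respondents the threshold moves: 17/22 (p=0.017) or 15/20 (p=0.041).

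**The case against.** A reader might infer that every subject who gained only for physical activity is counted as a social benefit, so that the proportion is inflated. The documents do not support that. The question joins the two areas with *and*, so such a subject may answer *less confident* or leave it blank, and a social-only gainer may do the same. The direction of error is unknown.

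Three further arguments deserve weight.

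- **Other items separate the two areas.** The HRQoL questionnaire (Appendix 1) has a physical-activity item under Confidence and a Social life group, and the OLI (Appendix 2) has items 11 to 18 on usual and social activities. Both are completed at Visits 1 and 2, and section 10.1 has individual questions listed and summarised. They allow a rough check on where a gain lies. They do not repair the endpoint: they are exploratory, use a seven-day recall, do not ask for a comparison with the usual product and are not mapped to it.
- **The 50% test may not apply.** Section 10.1 specifies it for yes/no answers and allows five-point answers to be grouped. This item is neither, so applying the test is an inference, though no other planned test fits a two-category answer better. All significance figures above depend on it.
- **The consequence is small.** This is one of 19 secondary endpoints in an exploratory study without formal hypotheses or success criteria, and no visible text proposes a social-only claim. That stands.

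The difference between increasing activities (label) and engaging in them (item) is minor, because the answers already compare confidence with the usual product. The missing *same* option is a separate weakness of this item. The sleep item below it has one.

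**Conclusion.** The point holds as a mismatch between endpoint and item. The one question mapped to the social-activity endpoint records social and physical gains in a single answer, so the reported proportion may lie above or below the social-activity proportion, by an amount the documents do not allow anyone to estimate. The mismatch itself needs no numerical assumption.

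The contrast between 18/25 and 17/25 shows only that one subject could matter, in either direction. It assumes that all 25 answer and that the 50% test is used for this item. It is not evidence that a result will be inflated.

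The importance is low. It affects what may be concluded from one secondary endpoint, and it matters only if a social-activity statement is drawn from it. The primary endpoint is unaffected.

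**What to change.** Choose one of the following:

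1. Delete the closing clause on physical activities from the Appendix 4 question, so that it matches the label in 5.3.
2. Keep the social question on its own and ask about physical activity as a separate Visit 2 item.
3. If the app question cannot be changed, relabel the endpoint in the synopsis, 5.3, 7.2 and the report as confidence to engage in social and physical activities, and make no separate social-activity claim from it.

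The first option costs one edited question in the clinical trial app. The second costs one more item for each subject at Visit 2. The third needs no new data. Section 12 gives changes to endpoints or assessment methods as examples of significant changes, so a notification to the ethics committee and the authority should be expected whichever is chosen. None of the three adds the missing *same* option; that would be a separate edit.
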